3.7.1.3. Imaging Outcomes

Imaging endpoints are: 1) infarct volume on MRI DWI sequence (or CT if MRI not feasible) 24 hours to 7 days after randomization; 2) lesion growth between the RAPID identified ischemic core on baseline imaging and the infarct volume; 3) successful reperfusion defined as DWI lesion volume minus $T_{max} > 6$ seconds greater than 50%; and 4) the proportion of subjects with recanalization of the primary arterial occlusive lesion. The technical efficacy of the endovascular procedure will be assessed by a modified Thrombolysis in Cerebral Infarction scores of 2b (50% to 75% reperfusion), 2c (>75% to 99% reperfusion) or 3 (complete reperfusion).²²

3.8. Clinical and Imaging Evaluations

Clinical assessments will be performed at baseline, 24 hours after randomization, hospital discharge, 30 days, and 90 days (Table 2). Clinical assessments include the modified Rankin Scale, the NIHSS, and quality of life measure (Neuro-QoL).²³

CT images will be read by appropriately trained clinicians as well as by the iSchemaView automated ASPECTS prior to randomization. ASPECTS for patient selection will be determined independently by the clinicians prior to any assessment with automated ASPECTS. In cases where there is disagreement, the physician reading will override the automated software reading. CTP images with mismatch determination will be read by iSchemaView automated RAPID software. All the images including baseline and follow-up MRI and CT images will be assessed independent of each other and blinded to treatment allocation at the core imaging laboratory at SELECT 2 Core Lab at McGovern Medical

SELECT 2 Protocol
4 August, 2021

School at UTHealth at Houston. Angiographic studies from the endovascular procedure will be assessed at SELECT 2 Core Lab.

3.9. Table 2. Schedule of Events

PROCEDURES	Screening	Enrollment	Baseline/ randomization	Thrombectomy	Day 1 (24 hrs +/-6 hrs)	5-7 Day follow- up (or discharge)	Day 30 (+/-15 days)	Day 90 (+/-15 days)	Day 365 (+/-60 days)
Screen Failure Log	X								
Inclusion and Exclusion Criteria	X								
Randomization			X						
Informed Consent		X							
Demographics			X						
Physical Exam ^a			X						
Vital Signs ^b			X						
Baseline Labs ^c			X						
Serum HCG (if applicable)			X						
Medical History			X						
Baseline Medications			X						
Baseline Characteristics			X						
NIHSS ^e			X		X	X			
Modified Rankin Scale ^d			X			X	X	X	X
Neuro-QoL ^d								X	X
Thrombectomy Timepoints/Procedural Data				X					
Post Treatment Hourly Blood Pressure Form (Treatment + 24 hrs) ^e			X	X	X				
Baseline Imaging (Head CT/CTA/CTP/MRI)			X						
Post Procedure Imaging (MRI 24 hours-7 days or CT if MRI not feasible)					X				
Image CRF completion by core lab (CT ASPECTS Score, CT Angio ASPECTS score, CT perfusion score, Angio mTICI, Capillary Index Score, Post-			X	X	X	X			

treatment/procedural, hemorrhage) ^f									
AE Reporting					X	X	X	X	
SAE Reporting					X	X	X	X	
Crossover explanations			X						
Protocol Deviation			X		X	X	X	X	

a. Physical exam at baseline as per standard of care (SOC). **b.** Vital Signs (BP and HR) recorded at baseline as per SOC. **c.** Labs (evaluation includes CBC with Platelets, Creatinine, Glucose, INR, activated PTT, and Pregnancy test (if applicable): at baseline as per SOC. **d.** If possible, 30 and 90-day visits should be completed in person. The telephone is allowed if the only option. **e.** for medical arm: recording blood pressure readings starts from either thrombolytics administration (if applicable) or randomization, for EVT arm recording blood pressure readings starts from the end of the thrombectomy procedure. **f.** Head CT/CTA/CTP/MRI: will be read centrally.

3.10. Assessment and Follow-up Visits

Baseline visit: The inclusion/exclusion page of the case report form must be completed to determine if the patient meets the eligibility requirements for the study. If the patient is eligible, then the consent form will be obtained by the patient or authorized representative.

24-hour visit (+/- 6 hours): The items listed for this visit in Table 2 should be performed between 18 and 30 hours from the time of the procedure.

Discharge visit: The items listed for this visit in Table 2 should be performed either on day 5/7 or the day of hospital discharge (whichever comes first).

30-day visit (+ / - 15 days): The items listed for this visit in Table 2 should be performed on day 30 (+/-15) days. The mRS score must be performed by an mRS certified evaluator who is blinded to treatment allocation. If possible, this visit should be completed in person. Telephone is allowed if the only option.

90-day visit (+ / - 15 days and preferably an in-person visit): The items listed for this visit in Table 2 should be performed on day 90 (+/- 15) days. The mRS score must be performed by an

mRS certified evaluator who is blinded to treatment allocation. The Neuro-QoL will also be completed on 90-day visit by an evaluator who is blinded to treatment allocation. If possible, this visit should be completed in person. Telephone is allowed if the only option.

365-day visit (+ / - 60 days): The mRS score must be performed by an mRS certified evaluator who is blinded to treatment allocation. The Neuro-QoL will also be completed on 360-day visit by an evaluator who is blinded to treatment allocation. Patients who were enrolled in the study at a date before the addition of the 365-day follow up visit, will be consented (remotely or in person) to complete the visit. The supplemental informed consent can be obtained verbally or in-written for patients who already provided their consents (or their LAR's consent) to participate in the study.

Neurological worsening: If clinical worsening (defined as a ≥ 4 point increase on the NIHSS score) occurs prior to discharge, a CT scan or MRI should be obtained as soon as possible. Neurological worsening is a reportable adverse event.

4. Sources of Materials

Information on the clinical status of patients will be obtained from the patient's medical record. Study coordinators at the site will complete the SELECT 2 case report forms to collect basic demographic and medical information about the patients. Data will subsequently be entered into the REDCAP electronic data capture system. Imaging data will be uploaded on DICOM (all patient identifiers are removed by the software prior to exporting the data outside of the site's firewall). All study sites will complete a screening log that documents all acute stroke patients treated by thrombectomy in the cath lab as well as patients who met the imaging criteria but were not enrolled in the study at their center, and the reason for exclusion of patients not enrolled. Serious adverse events (SAEs) will be reported within 24 hours of the event in the REDCAP electronic data capture system.

5. Site Approval and Monitoring Plan

Site approval: The University of Texas Health Science Center at Houston is the administration center and conducts data monitoring, core image lab reading and statistical analyses. Sites are selected for participation based on their experience in conducting clinical trials, their acute stroke treatment, and thrombectomy volumes, and only after an extensive discussion and vetting process by the principal investigator and documentation of interventionist experience, prior clinical trial enrollments, well-established research infrastructure, commitment to conducting clinical research, fast treatment times and efficient workflow. Sites will have a requirement of at least 100 thrombectomy procedures/year. Sites will commit to randomization and treatment criteria based on agreed upon contract. Selected sites will have access to emergent CT/CT perfusion and/or MR imaging 24/7. Prior to activating a site, we will verify that RAPID is functional at the site. Sites will be activated for enrollment after test cases processed with RAPID have ensured good quality maps.

Monitoring for imaging quality: The Imaging Core Lab will monitor image quality throughout the study. If significant inadequacies or protocol errors are noted at a site, enrollment will be halted. Enrollment will resume after all imaging problems have been resolved and repeat dummy runs have been obtained that demonstrate adequate image quality.

Monitoring for bias: A detailed site-monitoring plan has been developed to detect bias. This plan will protect the study from enrollment, randomization, and treatment bias. Sites will report their volume of endovascular stroke procedures (within 24 hrs) each month on a screening log. If a SELECT 2 eligible patient is treated with endovascular thrombectomy outside the SELECT 2 study, an explanation will be required detailing why the patient was not enrolled. The second component of the plan involves tracking of patients who are consented but not randomized. These patients will require an explanation of why the patient was not randomized as well as documentation whether endovascular thrombectomy was performed outside of the study. A third component involves monitoring of crossover after randomization. The Executive

Committee will review the data described above for each site every 6 months. If evidence of enrollment bias is suspected, it will be investigated. If confirmed, the site will be placed on probation. If additional incidents of suspected bias are confirmed, the site will be withdrawn. Routine monitoring of the clinical sites for the source to database verification will be performed by the UT Houston site.

6. Sample Size Calculation and Statistical Analysis Plan

6.1. Sample Size justification, Adaptive Enrichment Design, and Statistical Analysis Plan

The study will implement a novel adaptive enrichment design that will not only allow the trial to stop early for efficacy but also allow to select and evaluate the treatment effect in a most promising subpopulation if futility rule is triggered at the interim (or final) analyses in the overall population. This adaptive design has been developed, well-studied, and implemented for the DEFUSE 3 studies²⁴. The details and theory of this adaptive enrichment design are summarized in Lai et al (2014)²⁵ and Lai et al (2018)²⁶. This adaptive enrichment design is an extension of standard group sequential design with an enrichment feature²⁵. It will test for efficacy or futility with two interim analyses and a final analysis. This adaptive design was chosen because the preliminary data from the SELECT study suggest a potential heterogeneity in thrombectomy treatment effect based on the different imaging profiles. By adopting this adaptive design, we expect to reallocate future accrual and study treatment effects only in a most promising subpopulation when there is evidence to show that EVT is futile in the overall population at interim (or final) analyses. By limiting the subsequent enrollment only in the most promising subpopulation, a larger number of patients will eventually be enrolled in this subgroup for efficacy testing compared to traditional designs.

This design uses the Generalized Likelihood Ratio (GLR) statistic (Kullback-Leibler criterion) as criteria to identify the subgroup, which has the best chance of showing a benefit from EVT.

Through these criteria, it can achieve optimal balance simultaneously between the estimated size of the treatment effect and the sample size of the subgroup. By considering the CTP core volume and treatment time window, the patients are split into six disjoint groups, that is Group 1 (ASPECTS 3-5 and CTP/MRP core volume <50cc) at early time window 0-12 hours (denoted as **G1A**), Group 1 at late time window 12-24 hours (denoted as **G1B**), Group 2 (ASPECTS 6-10 and CTP/MRP core volume \geq 50cc) at early time window (denoted as **G2A**), Group 2 at late time window (denoted as **G2B**), Group 3 (ASPECTS 3-5 and CTP/MRP core volume \geq 50cc) at early time window (denoted as **G3A**), and Group 3 at late time window (denoted as **G3B**).

Considering a prior assumption that the EVT effect is largest in the patients with good imaging profile and treated within the shortest time window, we assume that the highest effect of EVT will be observed in G1A. Then the effects get decreased gradually in G1B, G2A, G2B, G3A, and the lowest effect will be observed in G3B. According to this adaptive design, when a most promising subgroup needs to be selected at the time of interim (or final) analysis, we will compare the GLR statistic among five cumulative groups, that is, G1A, G1A+G1B (i.e., Group 1), G1A+G1B+G2A, G1A+G1B+G2A+G2B (i.e., Group 1+Group 2), and G1A+G1B+G2A+G2B+G3A.

Primary analysis: The primary endpoint is the distribution of scores on the modified Rankin Scale (mRS) at day 90. The null hypothesis will be tested at the interim and final analysis using a normal approximation of the Wilcoxon-Mann-Whitney test (the GLR test). The principle of the intention to treat will be applied for the primary analysis. An additional analysis of the primary endpoint will be the same rank-based analysis comparing the 90-day mRs distribution between treatment groups while stratifying for prognostically important covariates. We will use the Generalized Cochran-Mantel-Haenszel test (CMH) to evaluate whether there is a uniform shift on the mRS distribution from one group to the other after stratification. The CMH test will be stratified by these variables used in the covariate adaptive randomization. For age, NIHSS, treatment time window, and CTP core volume, we will consider them as continuous variables in this adjusted analysis.

Power and sample size considerations Based on prior reported data, the following distributions were projected on the mRS at 90 days in EVT and MM groups for SELECT 2 in the overall population.

	mRS at day 90							Total
	0	1	2	3	4	5	6	
Endovascular group	4%	8%	12%	16%	19%	13%	28%	100%
Medical group	1%	4%	9%	14%	19%	10%	43%	100%

This distribution corresponds to a standardized effect of 0.34 for the primary analysis. Based on these data, the fixed sample size for a non-adaptive design requires a total of 376 patients (188/arm) to have 90% power at an alpha of 5% (Wilcoxon-Mann-Whitney test); We add additional 184 patients for the adaptive design to reach a maximum sample size of 560. We will conduct two interim analyses when we reach the number of patients at 200 and 380. Through extensive simulation studies, we have shown that with 560 patients in total for the adaptive design, we will have around 91% power to test for a standardized effect size of 0.34 in the overall population (assuming homogeneous EVT effect across six disjoint groups) by controlling an overall (one-sided) Type I error rate at 2.5%.

Efficacy and futility bound At each analysis (two interim analyses and the final analysis), an efficacy bound will be set to decide if the study should be stopped for efficacy while controlling the overall (one-sided) Type I error rate at 2.5%. At each interim analysis, a futility bound will be set to decide if the study should continue recruitment in the overall group, shift accrual and testing to a subgroup, or stop the trial entirely. When the futility bound is crossed and the optimal subgroup is selected, the maximum analyzed sample size will not be fixed but a random variable (smaller than the fixed maximum sample size 560). Due to the reduction in the maximum number of patients available for analysis at the end of the study, our design allows

an easier futility stop after subgroup selection. Further details regarding efficacy and futility bounds at interim and final analyses is provided in Appendix B.

First interim analysis (n=200 randomized and completed 90-day follow-up): The null hypothesis is tested in the entire patient cohort:

1. If neither efficacy nor futility bound is crossed, the trial continues enrollment to the 2nd interim analysis.
2. If the efficacy bound is crossed, the trial stops and efficacy is declared in the overall cohort.
3. If the futility bound is crossed, the optimal subgroup is selected based on the GLR statistic and the null hypothesis is tested in this selected subgroup:
 - 3.1. If neither bound is crossed, the trial will continue with enrollment limited to the selected subgroup
 - 3.2. If the efficacy bound is crossed, the trial stops and efficacy is declared in the selected subgroup
 - 3.3. If the futility bound is crossed, the trial stops for futility.

Note: the futility bound is relaxed as described above, based on the expected maximum number of patients in the trial at completion (i.e. 560 minus the number of patients already enrolled in the groups that will no longer be open for enrollment).

Second interim analysis (n=380 randomized and completed 90 day follow-up): After the first interim analysis, the trial proceeds to this stage under two scenarios: (1) continuing enrollment in the overall population (i.e., option 1 above) and (2) limiting enrollment to a selected subgroup (i.e., option 3.1 above). When scenario (1) happens, the testing at the 2nd interim analysis is identical to the first interim analysis. When scenario (2) happens, the null hypothesis is tested in that selected subgroup:

1. If neither bound is crossed, the trial continues to the final analysis with an enrollment of $560-380=180$ additional patients limited to the selected subgroup

2. If the efficacy bound is crossed, the trial stops and efficacy is declared in the selected subgroup
3. If the futility bound is crossed, the trial stops for futility.

Final analysis (n=560 randomized and completed 90-day follow-up): After the 2nd interim analysis, the trial proceeds to the final stage under two scenarios: (1) continuing enrollment in the overall population and (2) limiting enrollment to a selected subgroup.

When scenario (1) happens, the null is tested in the overall population:

1. If the efficacy bound is crossed, EVT is declared efficacious in the overall population.
2. If the efficacy bound is not crossed, the optimal subgroup is selected and the null is tested in that group:
 - 2.1. If the efficacy bound is crossed, EVT is declared efficacious in that subgroup
 - 2.2. If the efficacy bound is not crossed, EVT will be declared of no benefit.

When scenario (2) happens, that is, limiting enrollment to a subgroup (either selected at the 1st or 2nd interim analyses), the null hypothesis is tested in that selected subgroup only. Efficacy or lack thereof will be declared as per options 2.1 and 2.2 above.

Operating characteristics of the adaptive design: We have conducted simulations (5000 simulated trials) to evaluate the performance of the adaptive design (max n=560) and compare it to a traditional fixed sample-size design (fixed n=560) under various scenarios (see **Table 3**, below). For the simulations the effect size is expressed as a standardized effect with normal approximation, where a standardized effect of 0.32 or 0.30 corresponds to a conservative projected effect of EVT (anticipated effect 0.34; see section of Power and sample size considerations). We assume that we will observe the number of patients in G1A, G1B, G2A, G2B, G3A, G3B with 14%, 6%, 14%, 6%, 42%, and 18%, respectively.

Scenario	Standardized effect in groups G1A, G1B, G2A, G2B, G3A, G3B							Average standar d. effect	Adaptive Design		Fixed Design	
									Average No. randomized	Power	Number randomized	Power
#0	0	0	0	0	0	0	0	0	426	2.0%	560	2.5%
#1	0.32	0.32	0.32	0.32	0.32	0.32	0.32	0.32	376	86.0%	560	95.8%
#2	0.3	0.3	0.3	0.3	0.3	0.3	0.3	0.3	393	81.1%	560	93.3%
#3	0.4	0.4	0.4	0.4	0	0	0.16	0.16	500	74.1%	560	45.7%
#4	0.4	0.4	0.4	0.4	-0.1	-0.1	0.1	0.1	502	78.5%	560	21.2%
#5	0.4	0.4	0.3	0.3	0	-0.1	0.122	0.122	513	67.1%	560	29.2%
#6	0.5	0.5	0	0	0	0	0.1	0.1	503	70.6%	560	21.2%
#7	0.5	0	0	0	0	0	0.07	0.07	503	60.5%	560	12.8%

Table 3. Under the null (Scenario #0), the adaptive design controls the total Type 1 error below 2.5%, stops early for futility 59.1% of the time, and the average number of randomizations is 426. If the effect is uniform across cells at 0.32 (scenario #1), the fixed-sample design is optimal, but the adaptive design results in only a small loss of power (from 95.8% to 86.0%), but reduced the expected sample size (from 560 to 376). We observed similar findings when the effect is uniform across cells at 0.3 (scenario #2). The adaptive design performs much better (higher power and smaller expected sample size) than the fixed-sample design when the effect size distribution across the subgroups is in accord with the biological assumptions (scenarios #3, #4 and #5). If the effect is concentrated only in Group 1 (scenario #6) or Group 1A (scenario #7), the adaptive design maintains power (70.6% in scenario #6 and 60.5% in scenario #7) while the conventional design collapses (21.2% power in scenario #6 and 12.8% in scenario #7).

Secondary analyses: Our secondary endpoint is the proportion of patients with mRS 0-2 at day 90 (indicating functional independence). The difference in the proportions of patients with mRS 0-2 between treatment arms will be assessed using logistic regression. We will adjust for the variables we used in adaptive randomization program in the logistic regression model. Other secondary endpoints include (1) the safety outcomes measured by the incidence of sICH, neurological worsening, mortality, groin hematomas, infections or vascular injury, (2) infarct volume, lesion growth, successful reperfusion, and recanalization rate, (3) length of hospital stay, and (4) discharge disposition. The exploratory analyses on secondary outcomes will include descriptive statistics (mean [\pm standard deviation, SD] or median and interquartile range for continuous variables and frequency [percentage] for discrete variables) and appropriate test for secondary outcome variables between two groups. For binary outcomes (e.g., sICH, neurological worsening, mortality, groin hematomas, infections or vascular injury, successful reperfusion, recanalization), Chi-square or Fisher's exact test where appropriate will be used to compare the incidence between two treatment groups for large core patients. We will also apply the logistic regression model on these outcomes after adjusting for the variables we used in adaptive randomization program. The adjusted odds ratio (OR), as well as 95% confidence interval will be reported. For the length of stay, mean \pm SD and median (Interquartile range) will be calculated for each group. For continuous variables (e.g., the length of stay and infarct volume), two sample t-test or Wilcoxon rank sum test as appropriate will be applied to compare them between two groups. For discharge disposition, frequency and percentage of each disposition will be reported and Chi-square test or Fisher's exact test where appropriate will be applied to compare its distribution between two groups.

Subgroup analyses: Subgroup analyses of the effect of thrombectomy on the primary and secondary endpoints will be performed. Subgroups will be defined based on the stratification variables, key demographic factors (such as race and ethnicity), thrombolysis vs. no thrombolysis, CTP vs. MRI selection, and witnessed vs. unwitnessed symptom onset, wake-up vs non-wake-up stroke, and TIC1 0-2a vs. TIC1 2b/3 results in the cath lab. An additional

subgroup analysis will be performed in patients who present with extracranial ICA occlusion. Also, an additional subgroup analysis will be performed in patients based on thrombolytic therapy received.

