After obtaining consent and ensuring all inclusion and exclusion criteria are met, randomization will be done in the emergency room prior to treatment using a web-based dynamic randomization system. Our randomization algorithm will be accessible to the study investigators and staff through a separate web page accessible only through the REDCAP database module. Covariate adaptive randomization will be used to balance the distribution of age (<60, 60-69, 70-79, 80-85 years old), presentation NIHSS (6-9, 10-15, 16-20, >20), center, clot location (M1, ICA), treatment time window (0-8, 9-16, 17-24 hours from onset to randomization time), CTP/MRP core volume (<50cc, 50-100cc, >100cc), presence or absence of target mismatch profile (mismatch ratio ≥ 1.8 & mismatch volume ≥ 15 cc) and hemisphere (right, left) between the two treatment groups.

The randomization algorithm we are going to implement is the algorithm developed by Pocock and Simon (1975)²⁷, i.e., minimization method. Through this algorithm, the assignment of a new patient to a treatment group is determined so as to minimize the differences between the groups in terms of these important key baseline variables. Unlike traditional stratified randomization, the minimization method works toward minimizing the total imbalance for all factors together instead of considering mutually exclusive subgroups, that is, we will not be creating these mutually exclusive subgroups during the randomization. Therefore, this approach is not restricted by the number of variables and the possible combinations of levels of balancing factors. Further details about Randomization can be found in Appendix A.

Eligible patients will be randomized into thrombectomy plus medical management vs medical management alone at a 1:1 ratio. The minimization algorithm is intended to balance the baseline characteristics between the two study arms, thrombectomy vs. medical management. The algorithm is not intended at the level of imaging profile subgroup. When a new patient is enrolled, the site will enter the stratification factor values into the dynamic randomization webpage and the treatment assignment will be determined immediately. An emergency 1-800 number will be provided if web-based randomization is not available due to exigent circumstances.

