Appendix B. Efficacy and futility bounds for interim and final analysis

At the l th interim analysis, let W_i^l be the sum of the ranks of Rankin scores from the endovascular group in the patient subgroup Π_i , $j = 1, \dots, J$. In our trial, we defined $J = 6$ groups with Π_j denotes the entire patient population and Π_1, \dots, Π_5 denote the subgroups of G1A, G1A+G1B, G1A+G1B +G2A, G1A+G1B +G2A +G2B, G1A+G1B +G2A +G2B +G3A, respectively.

The standardized Wilcoxon statistic for patient subgroup Π_i is

$$Z_i^l = \left\{ W_i^l - \frac{n_i^l(n_i^l + n_{0i}^l + 1)}{2} \right\} / \left\{ \frac{n_i^l n_{0i}^l (n_i^l + n_{0i}^l + 1)}{12} \right\}^{1/2},$$

where, n_i^l and n_{0i}^l denote the numbers of patients enrolled into the endovascular group and medical management group at the l th interim analysis, respectively.

At the l th interim analysis, we will terminate the trial and claims efficacy for the endovascular group if the following efficacy bound is crossed, that is,

$$Z_j^l \geq b.$$

Otherwise, we will proceed to the subgroup selection if the following futility bound is crossed, that is,

$$\widetilde{Z}_j^l \leq \widetilde{b},$$

where

$$\widetilde{Z}_j^l = \left\{ W_i^l - \frac{n_i^l(n_i^l + n_{0i}^l + 1)}{2} - n_i^l n_{0i}^l \theta \right\} / \left\{ \frac{n_i^l n_{0i}^l (n_i^l + n_{0i}^l + 1)}{12} \right\}^{1/2}.$$

When the above criteria is satisfied, a subgroup \hat{I} with the largest value of Z_i^l for $i \neq J$ is chosen. The future enrollment of the trial will include patients of this subgroup only, while the maximum total sample size is still $N=560$.

Similar to testing the efficacy and futility in the entire population, at stage l' , we will terminate the trial and claim efficacy for the endovascular group in this selected subgroup if the following efficacy bound is crossed

$$Z_j^{l'} \geq b.$$

We may also terminate for futility if

$$\widetilde{Z}_j^{l'} \leq \widetilde{b}.$$

If neither the efficacy nor futility bound for the entire population ever occurs, the trial proceeds to the final stage and we terminate the trial and claim efficacy for the endovascular group if

$$Z_j^{l=3} \geq c.$$

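### The primary Wilcoxon test ignores the prognostic factors used for minimisation, which makes it mildly conservative in the overall population and gives up a modest amount of power

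*Combined protocol and SAP*

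**What the plan says.** - **Primary test.** Section 6.1 tests the null hypothesis at each look "using a normal approximation of the Wilcoxon-Mann-Whitney test (the GLR test"). Appendix B gives the formula under "The standardized Wilcoxon statistic for patient subgroup": a centred rank sum divided by a variance that depends only on the two arm sizes. The bounds are b = 2.604, futility −1.897 and c = 2.772.
- **Allocation.** The randomization text (Section 3.3, continued after the remote-consent procedure) says: "Covariate adaptive randomization will be used to balance the distribution of age", followed by NIHSS, center, clot location, time window, core volume, target mismatch and hemisphere. Appendix A sets the biased-coin probability at 0.9 and gives age and NIHSS the largest weights.
- **Adjusted analysis.** Section 6.1 adds: "An additional analysis of the primary endpoint will be the same rank-based analysis", done "while stratifying for prognostically important covariates". It continues: "The CMH test will be stratified by these variables used in the covariate adaptive randomization". The next sentence treats age, NIHSS, time window and core volume as continuous. This analysis appears nowhere in Appendix B.
- **Design figures.** The fixed design "requires a total of 376 patients (188/arm) to have 90% power at an alpha of 5"%. The adaptive design is said to have about 91% power at a maximum of 560 patients, "by controlling an overall (one-sided) Type I error rate at 2.5"%.

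**The concern.** Minimisation forces the arms to be alike on the listed factors. If those factors predict mRS, part of the outcome variance can no longer appear as a chance difference between arms. The unadjusted Wilcoxon variance still counts that part, so in the overall population its Z varies less than a standard normal under the null. The true error rate then lies below its target, and some power is lost. An adjusted test restores the correct spread. It also gains precision from the explained outcome variance, and it does so even where minimisation has not produced balance. Every covariate needed is already recorded at randomization. What is at stake is efficiency: power, and the number of patients needed to reach a decision.

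**Working it through.** **1. The plan's own figures.** From the projected mRS table in Section 6.1, P(EVT better) + ½P(tie) = 0.59375. The pooled tie factor is 1 − Σp³ = 0.942.

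N = (1.960 + 1.282)² × 0.942 / [3 × (0.59375 − 0.5)²] = 10.507 × 0.942 / 0.02637 = 375.4, so 376 as stated.

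Theta in Appendix B is 3.2415/√(3 × 560) = 0.0791, also as stated. A normal-approximation simulation of the Appendix B rules (20,000 trials) at effect 0.34 gives 91.1% power for a win in the overall population. It gives 2.1% rejection under the null, against the 2.0% in Table 3.

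**2. Prognostic strength.** No R-squared is given. Section 1.5 reports good-outcome rates of 48%, 32% and 20% for the three imaging profiles that correspond to Groups 1, 2 and 3. With the Section 6.1 shares of 20/20/60%, the between-group variance on the probit scale is 0.099, so latent R-squared = 0.099/1.099 = 0.09. Part of this reflects ASPECTS, which is not a minimisation factor. Splitting on core volume alone gives 48% against (20 × 32% + 60 × 20%)/80 = 23%, and a latent R-squared of about 0.07. Age and NIHSS come on top, by an amount the documents do not state. The range of 0.1 to 0.3 is an assumption.

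**3. Size in the overall population.** With perfect balance the null SD of Z would be roughly √(1 − R²), that is 0.95, 0.89 and 0.84 at R² = 0.1, 0.2 and 0.3. The Appendix A minimisation was then simulated (8,000 trials per setting). Assumptions: 30 centers, a mismatch weight of 2 because none is legible, medical-arm mRS cut-points, and a latent shift of 0.36. That shift gives a mean Z of about 3.9 at n = 560, against 3.96 from the projected table. Both tests are tie-corrected, so the differences come from the covariates. Power is for the overall-population path over looks at 200, 380 and 560 with the Appendix B bounds.

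| Assumed R² | Null SD, unadjusted Z (n = 560) | Power, unadjusted | Power, rank ANCOVA | Forgone |
|---|---|---|---|---|
| 0 | 1.01 | 89.2% | 89.5% | 0.3 |
| 0.1 | 0.95 | 90.5% | 92.9% | 2.4 |
| 0.2 | 0.91 | 91.7% | 95.4% | 3.7 |
| 0.3 | 0.87 | 92.3% | 97.2% | 4.9 |

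A separate simulation gave 89% to 91% at R² = 0.1 and 91% to 95% at R² = 0.25.

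**4. Full rule, including subgroup selection.** With the bounds unchanged and R² = 0.1/0.2/0.3, overall type I error was 1.8/1.6/1.1% unadjusted and 2.4/2.5/2.7% adjusted (20,000 trials each). With an effect only in Groups 1 and 2 (similar to Scenario #3; assumed latent shift 0.42; 4,000 trials), power was 76/77/76% against 82/86/91%. The plan's own figure for Scenario #3 is 74.1%. The gain there is probably larger than under a uniform effect, but this rests on one simulation.

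**5. Selected subgroups.** At assumed R² = 0.25 (4,000 null trials), the SD of the unadjusted Z at n = 200/380/560 was:
- Overall: 0.92/0.91/0.91
- G1A: 1.02/0.99/0.99
- Group 1: 1.01/1.00/1.00
- Groups 1+2: 0.98/0.96/0.96

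**6. The planned CMH.** The minimisation categories without center give 4 × 4 × 2 × 3 × 3 × 2 × 2 = 1,152 cells for at most 560 patients, or 0.49 patients per cell. Most strata would be empty or hold one patient and contribute nothing. Treating four of the same factors as continuous is a different method from stratifying on them, and the plan does not say how the two are combined.

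**The case against.** The strongest reply is that nothing promised is missed. The sample size and power were derived for the unadjusted test, and they reproduce. Conservatism is not a failure of error control. An adjusted analysis is already prespecified, and the unadjusted statistic is tied to the cited enrichment method. All of this stands except the reliance on the adjusted analysis, which plays no part in any decision and is unworkable as written.

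Three stronger readings are tempting, and the documents do not support them:

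- **That the conservatism is worst in small selected subgroups and at interim looks.** The randomization text says the algorithm is not aimed at the imaging-profile subgroups. Marginal balance overall leaves covariates almost free within G1A or Group 1, where the Z is close to nominal (step 5). The overall Z is no more conservative at 200 than at 560. Any gain in subgroups comes from explained outcome variance.
- **That the trial is underpowered.** At the plan's projected effect the unadjusted test delivers about the stated power. A much lower figure appears only if a smaller effect is assumed.
- **That the existing bounds carry over untouched.** The futility statistic subtracts a theta drift and divides by the Wilcoxon variance, so a smaller adjusted variance changes the standardised drift, and with it subgroup selection and Table 3. In G1A at the first look (14% of 200 = 28 patients) the adjusted Z had an SD of about 1.1. The 2.7% in step 4 is also slightly high.

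Error rates computed at a cut-off of 1.96 would not describe this trial, which uses sequential bounds. Step 4 therefore gives the rates under the full rule.

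**Conclusion.** The point holds as a matter of efficiency. In the overall population the unadjusted primary test is mildly conservative under the planned minimisation: null SD of Z about 0.95 to 0.87, and about 2 to 5 points of power forgone on the overall-population path. A larger gain is likely when the effect is confined to some imaging groups. The size depends on an assumed latent R-squared of 0.1 to 0.3. The documents' own figures support only about 0.07 to 0.09 from imaging, so the lower end is the cautious reading. If the factors prove uninformative, adjustment costs almost nothing (89.2% against 89.5%). The change is worth making because the data are already collected. It corrects no validity failure: the 376 patients and the 90–91% power stand, and type I error is not inflated.

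**What to change.** 1. Make the primary statistic, overall and in each nested subgroup, a prespecified rank ANCOVA: regress mid-ranks of 90-day mRS on age, NIHSS, time and core volume (continuous), occlusion site and target mismatch, and test treatment. Below a stated subgroup size, limit the covariates to age and NIHSS.
2. Re-run the Table 3 simulation with this statistic under the Appendix A minimisation. Confirm or slightly recalibrate b, c and the futility bound, including the theta drift under the adjusted variance.
3. Report the unadjusted Wilcoxon as a sensitivity analysis. Drop the CMH analysis, or restate it with a few named strata.

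The cost is SAP and Appendix B wording, one simulation re-run and possibly slightly different bounds. No extra patients or data are needed. The remaining risk is slight anti-conservatism in very small subgroups, which the shorter covariate list is meant to limit and the re-run should check.
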